Study Protocol & Statistical Analysis Plan

Title: Feasibility of Gamma Transcranial Alternating Current Stimulation to Reduce Beta-amyloid Load and Improve Memory

NCT#: NCT04646499

Last Updated: 11/02/2021

Participants.

This study was preregistered at ClinicalTrials.gov with identifier NCT04646499. The study protocol was approved by the University of California San Francisco (UCSF) Institutional Review Board and all participants signed informed consent documents prior to participating in the study. Participants received \$20 per hour for participation and a \$50 bonus for completion of the study. To be eligible for this study, all participants were 60-80 years of age, fluent in English, had at least 12 years of education, and had normal or corrected-to-normal vision. In addition, participants had to have aMCI (see below for aMCI inclusion criteria) and be able to complete cognitive tasks and cooperate with all study procedures. The exclusion criteria were as follows: neurological or psychiatric disorders other than aMCI, receiving investigational medications or participated in a clinical trial with medications within the previous 30 days, family history of epilepsy, implanted electronic devices (e.g. pacemaker), prior serious head trauma, pregnant, or IQ under 80. In addition, participants were not on cholinesterase inhibitors, memantine, psychotropics, anti-depressants, or anti-anxiety medications. Finally, participants did not have color vision deficiency, a history of substance abuse, glaucoma, macular degeneration, amblyopia, or strabismus.

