Fourteen older adults with aMCI were enrolled and 13 completed the entire intervention in a single-arm design (age mean: 73.62 years (SD: 5.44), Montreal Cognitive Assessment mean (MoCA): 23.39 (SD: 3.66), Education years mean: 17.69 (SD: 2.78), 7 Male, 11 right-handed). Prior to enrolling in the study, all participants completed the Montreal Cognitive Assessment (MoCA). In the current study, participants were considered aMCI by scoring between 27 and 16 on the MoCA and had a self-complaint of memory difficulty. In addition, participants needed an age-matched Z-score of at least -1 on immediate memory or delayed memory (as measured by the California Verbal Learning Test, short version) and at least -1 Z-score on verbal fluency (D words), semantic fluency (animals), processing speed (digit symbol and number trails tasks), or task switching (number letter trails task). All participants also scored as having intact activities of daily living by scoring as mostly independent on the IADL. Finally, all participants had the presence of both AB and tau in the pre-tACS phlebotomy biomarker analyses, indicating that MCI status is likely due to progression towards AD as opposed to other potential causes of cognitive decline. One participant withdrew voluntarily prior to any cognitive assessment or tACS.

Study Timeline.

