The study required 10 visits to UCSF over 5 weeks. During visit 1, participants completed baseline assessments of the instrumental activities of daily living (IADL) survey, cognitive tests assessing baseline episodic memory performance, and an MRI scan (Week 1). On the following week, participants received gamma tACS while engaged in the Stimulation Tasks (see details below) on five consecutive weekdays (Week 2, visits 2-6, Monday-Friday). On one day during each of the three following weeks, participants also completed the Stimulation Tasks while receiving gamma tACS (Weeks 3-5, visits 7-9). These sessions occurred on the same day of the week for each participant (e.g. consecutive Tuesdays), with a small number occurring \pm one day. Finally, during the 5th week (visit 10), participants completed the same procedure as the baseline assessment (visit 1), which included the IADL survey, tests of episodic memory, and an MRI scan. All study activities took place at UCSF, except for one participant who completed the eight tACS sessions in their home. For this participant, a researcher was present with the required tACS equipment during the at-home sessions, and the participant completed the MRI and outcome assessments at UCSF.

Surveys.

Participants completed the Instrumental Activities of Daily Living (IADL) during the initial pre-tACS and post-tACS follow-up Cognitive Task sessions (Weeks 1 and 5, respectively). Additionally, following each tACS session, participants filled out a tolerability survey of the following 11 measures on a scale of 0 (not noticeable) to 10 (not tolerable): headache, neck pain, scalp pain, tingling, itching, burning sensation, increased alertness, increased sleepiness, trouble concentrating, acute mood change, and presence of phosphenes. Prior to the initial tACS session (Week 1) participants completed surveys that measure their anticipation, anxiety, and expected benefits on both memory and cognition following tACS on a scale of 1 - 10. Following the final tACS session (Week 5), participants were probed on the same categories for their perceived benefits of the tACS intervention.

Magnetic Resonance Imaging.

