Our primary outcome measures were feasibility and tolerability of eight sessions of gamma tACS. To assess these, we measured dropout rate of participants and the reported side effects collected following each stimulation session. Analysis of the side effects collected following the end of tACS consist of the average across all 8 sessions for the 11 potential categories. These metrics were rated on a scale of 0 (not noticeable) to 10 (not tolerable). As this was a single-arm design, we compared side effect ratings from this study to those from a recently completed a multi-session tACS intervention in healthy older adults of the same age range, in which we administered 1 mA of 6 Hz tACS to the prefrontal cortex (F3-F4, 10-20 EEG system). This allows for an age-matched comparison between prior stimulation protocols and one that is higher in dose (1 mA vs 1.6 mA), frequency (6 Hz and 40 Hz), and duration (~20 minutes and 60 minutes) employed in the current study. As both studies included the same side-effects questionnaire categories, we conducted a non-parametric Mann-Whitney U test to assess differences in the average ratings for each metric between the two studies.

Secondary Behavioral Outcomes.

Secondary outcome measures assessed changes in performance on the memory and fluency tasks (CVLT, PAT, fluency). The CVLT is a standardized cognitive test with different task demands at each stage. For CVLT, we focused on the correct items named during the short-delay free recall (SDFR) and long-delay free recall (LDFR) sections. For the PAT, we measured accuracy for both the recall and recognition portions. For the semantic (animals) and verbal (F, A, S) fluency task, we measured the number of correct non-repeated words.

Secondary Phlebotomy Outcomes.

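### The cross-study test of side-effect ratings cannot support an inference about the stimulation protocol, because diagnosis and study are completely aliased with protocol

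*Combined protocol and SAP*

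**What the plan says.** Under Primary Outcomes: "Our primary outcome measures were feasibility and tolerability of eight sessions of gamma tACS". These are assessed by dropout and by ratings taken after each session, averaged over the eight sessions for each of 11 categories, on a scale anchored at 0 (not noticeable) and 10 (not tolerable).

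Because there is no control arm, the same section adds a Mann-Whitney U test of each mean rating against an earlier study. That study gave 1 mA at 6 Hz over F3-F4 and is described as "a multi-session tACS intervention in healthy older adults of the same age range". The next sentence reads: "This allows for an age-matched comparison between prior stimulation protocols", and goes on to contrast these with the current protocol. It lists three differences: dose (1 against 1.6 mA), frequency (6 against 40 Hz) and duration (about 20 against 60 minutes).

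Under Participants: "Fourteen older adults with aMCI were enrolled and 13 completed the entire intervention in a single-arm design". On classification, "participants were considered aMCI by scoring between 27 and 16 on the MoCA and had a self-complaint of memory difficulty", with further criteria on memory and on fluency, processing speed or task switching. On age, "all participants were 60-80 years of age".

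Under Surveys, six of the 11 items are pain or skin sensations. The rest are "increased alertness, increased sleepiness, trouble concentrating, acute mood change, and presence of phosphenes".

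The plan describes no matching procedure, covariate adjustment, sensitivity analysis or caveat for this comparison.

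**The concern.** The comparison is framed as one between protocols in groups alike in age. In fact the groups differ in diagnosis and come from different studies, and the listed differences include neither. Ratings such as trouble concentrating could differ between people with aMCI and healthy people whatever stimulation they receive. Cognitive status might also alter how sensations are noticed or reported.

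This is the only hypothesis test described for a primary outcome. A significant result could be read as showing that the stronger, longer protocol is less well tolerated. A non-significant one could be read as showing that it is tolerated just as well. Neither reading would be justified.

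**Working it through.** The plan gives no sample size, power, margin or expected difference for this comparison, so there is no figure to reproduce. The main check is structural; the calculations that follow are illustrative.

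**1. Who received what**

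| | Current study | Earlier study |
|---|---|---|
| Diagnosis | aMCI, all participants | Healthy |
| Protocol | 1.6 mA, 40 Hz, 60 min, eight lateral sites | 1 mA, 6 Hz, about 20 min, F3-F4 |
| Age | 60-80; mean 73.62 (SD 5.44) | Same range; distribution not given |
| Number | 14 enrolled, 13 completed | Not given |

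**2. What the contrast estimates**

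Let a mean rating shift by P for the new protocol, D for aMCI and S for study. The two off-diagonal cells (aMCI with the old protocol, healthy with the new) are empty, so the indicators for protocol, diagnosis and study are identical for every person. The difference between groups estimates only P + D + S. No adjustment within these data can recover P.

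**3. Age**

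A shared range does not fix the distribution. For illustration, a comparator group spread evenly over 60-80 would average (60 + 80)/2 = 70 years, which is 73.62 − 70 = 3.62 years below the current sample. The groups may in fact be close in age, but the documents do not show it.

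**4. What a diagnosis shift would do, if there were one**

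Assumptions not taken from the documents: comparator n, size of shift, normal ratings with SD 1, two-sided α = 0.05. The figures are per rating, with n₁ = 13.

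Normal approximation, with Mann-Whitney efficiency 0.955:

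rejection ≈ Φ(δ·√(0.955·n₁n₂/(n₁+n₂)) − 1.96)

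- n₂ = 20: √(0.955 × 260/33) = 2.743. For δ = 0.5, Φ(−0.588) = 27.8%. For δ = 0.8, Φ(0.234) = 59.3%.
- n₂ = 30: √(0.955 × 390/43) = 2.943. For δ = 0.5, Φ(−0.488) = 31.3%. For δ = 0.8, Φ(0.394) = 65.3%.

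Simulation of the test itself (4,000 replicates; n₂ = 13, 20 and 40; range across the three):

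| Protocol effect (SD) | Diagnosis shift (SD) | Trials with p < 0.05 |
|---|---|---|
| 0 | 0 | 4-5% |
| 0 | 0.3 | 10-14% |
| 0 | 0.5 | 20-32% |
| 0 | 0.8 | 46-66% |
| 0.8 | 0 | 46-66% |
| 0.8 | −0.5 | 10-14% |
| 0.8 | −0.8 | 4-5% |

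The test responds only to the sum. A diagnosis shift of 0.8 SD with no protocol effect looks the same as a protocol effect of 0.8 SD with no diagnosis shift. An opposite shift can hide a real protocol effect.

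**The case against.** The strongest reply is that little depends on this test. Dropout and the within-study mean ratings are already specified as measures of the primary outcomes, and no success criterion, margin or decision rule uses the cross-study result. The comparator is openly called healthy, the test itself is described as a comparison between studies, and the plan nowhere claims equal tolerability. The trial is labelled a hypothesis-generating pilot. All of this stands, and it limits the point to how the comparison is labelled and read.

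The route from diagnosis to ratings is also narrower than it may seem. Three of the four cognition or mood items (alertness, sleepiness, mood) are worded as change, which partly answers the lack of a pre-session rating. Seven of the 11 items are sensations, including phosphenes. Ratings are collected after each session, which limits demands on recall. Other neurological and psychiatric disorders and psychotropic drugs are exclusions. This reduces the plausible bias but does not remove the aliasing.

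A reader might infer that at least five factors are confounded: diagnosis, current, frequency, duration and montage. The documents do not support that count. The last four together make up the protocol, and the plan does not claim to isolate any of them. Their joint change does not confound a comparison of whole protocols. Diagnosis and study do.

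Disclosing the word healthy does not settle the matter, because the sentence that follows presents the contrast as age-matched and between protocols and does not name diagnosis among the differences. The pilot label is used in the plan to justify leaving multiplicity uncorrected. It does not make the two groups comparable.

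**Conclusion.** The point holds as one about interpretation. Diagnosis and study are completely aliased with protocol, so no result of the Mann-Whitney tests can be assigned to the stimulation protocol. This follows from the design and needs no numerical assumption. The age-matched description rests on a shared range only.

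The size and direction of any bias cannot be determined from the documents. The rejection rates above depend on an assumed comparator size, shift and distribution. They show what a shift would do, not that one exists.

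Two stronger readings should be resisted. One is that the primary tolerability outcome is invalid: dropout (1 of 14, 7.1%) and the eight-session mean ratings are within-study measures and are untouched. The other is that aMCI has distorted the ratings: nothing in the documents shows that it moves them by any amount. The matter is worth correcting because it changes what may be concluded from the one test on a primary outcome, at almost no cost.

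**What to change.** Under Primary Outcomes:

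- Rest the tolerability conclusion on the measures already specified there: dropout, and the eight-session mean ratings read against the 0-10 anchors.
- Report the cross-study Mann-Whitney comparison as descriptive context, with no inference about the protocols from either a significant or a non-significant result.
- Replace the age-matched wording with a statement that the groups share an age range, unless the two age distributions are shown to match.
- State that the groups differ in diagnosis and come from separate studies, and add electrode montage to the listed protocol differences.

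Reporting the cognition and mood items separately from the sensation items is optional.

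The cost is wording only; no new data are needed. The small downside is that the sponsor gives up an inferential claim about the tolerability of one protocol against the other.

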During the final 10 minutes, participants completed three MDT test blocks where they viewed 13 items seen during encoding, 13 items that were an alternate (similar) version of the encoded items, and five novel lures. For each item participants responded as to whether they were the same exact item from the encoding task from the beginning of stimulation. Each item was viewed for 2500 ms and followed by a screen where participants would respond whether the item was definitely old (“D” key), maybe old (“F” key), maybe new (“J” key), or definitely new (“K” key). A fixation cross was presented on the screen for 1000 ms between trials. The order of the target, lure, and novel items was random within each of the three testing blocks. In total, the tasks for the participant to complete during stimulation are equal to the length of the tACS session (1 hour).

Data Processing and Statistical Analysis.

Given the relatively small number of participants this study, we used non-parametric tests for all statistical analyses to reduce influence from potential extreme values. Changes in outcome metrics were assessed with non-parametric Wilcoxon sign-ranked tests. We also report rank-biserial correlations (r_{rb}) to represent effect sizes of these changes, similar to Cohen's d . We set a significance threshold of $p < 0.05$ and report non-significant 'trends' at $p < 0.10$. As this is a hypothesis-generating pilot study, we did not correct for multiple comparisons for each test conducted.

Primary Outcomes.

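### The primary tolerability comparison is 11 difference tests with no estimate or interval, so with 13 stimulated participants a non-significant result is weak evidence of comparable tolerability

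*Combined protocol and SAP*

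**What the plan says.** The Primary Outcomes section of the combined protocol and SAP names feasibility and tolerability as primary. To assess them, "we measured dropout rate of participants and the reported side effects collected following each stimulation session". The side-effect summaries "consist of the average across all 8 sessions for the 11 potential categories", each rated from 0 (not noticeable) to 10 (not tolerable).

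Because the trial has one arm, the ratings are set against an earlier study by the same group, with its cortical target at F3-F4: "multi-session tACS intervention in healthy older adults of the same age range, in which we administered 1 mA of 6 Hz tACS to the prefrontal". For that comparison, "we conducted a non-parametric Mann-Whitney U test to assess differences in the average ratings for each metric between the two studies". The earlier study's sample size is not given.

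The Data Processing and Statistical Analysis section sets the threshold at p < 0.05, reports trends at p < 0.10 and, citing the hypothesis-generating pilot status, states that "we did not correct for multiple comparisons for each test conducted". It promises rank-biserial effect sizes, but for the pre-post changes, and mentions no intervals.

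On numbers, the Participants section says: "Fourteen older adults with aMCI were enrolled and 13 completed the entire intervention in a single-arm design". It adds: "One participant withdrew voluntarily prior to any cognitive assessment or tACS".

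**The concern.** The useful question about a stronger, longer protocol is how much worse its side effects could be than those of a milder one. A test of difference does not answer that when it is non-significant: the p-value alone does not separate ratings that are alike from ratings too few to compare. An estimate with an interval does. The plan provides neither for this comparison, and it states no tolerability criterion or acceptable dropout rate that would tell a reader how to use the p-values.

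At stake is how the primary outcome is interpreted. With 13 stimulated participants, a row of non-significant tests could leave room for a material worsening, and nothing in the planned report would show how much room.

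**Working it through.** The documents give no power, margin, rating SD or sample-size figure, so there is no stated figure to reproduce.

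**Inputs from the documents.** 14 enrolled and 13 completed. The one withdrawal came before any tACS, so 13 were stimulated and none of those dropped out. There are 11 categories, tested at alpha 0.05 without correction.

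**Assumptions.** Two-sided tests (sidedness is not stated), normal scores, comparator size n2 from 13 to 60, and effects in SD units.

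**Sensitivity of one test.** In SD units, SE = sqrt(1/13 + 1/n2), and power is approximately Phi(d/SE - 1.96). For n2 = 13, SE = 0.392; with d = 0.5, Phi(1.275 - 1.96) = Phi(-0.685) = 25%. The Mann-Whitney test was also simulated on normal data (4,000 runs per cell). The smallest worsening detectable with 80% power is (1.96 + 0.842) × SE. The 95% CI half-width is 1.96 × SE. Power is shown as approximation / simulation.

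| n2 | SE | Power, 0.5 SD | Power, 0.8 SD | Power, 1.0 SD | Detectable at 80% | CI half-width |
|---|---|---|---|---|---|---|
| 13 | 0.392 | 25% / 20% | 53% / 46% | 72% / 66% | 1.10 SD | 0.77 SD |
| 20 | 0.356 | 29% / 25% | 61% / 56% | 80% / 75% | 1.00 SD | 0.70 SD |
| 30 | 0.332 | 32% / 29% | 67% / 63% | 85% / 79% | 0.93 SD | 0.65 SD |
| 60 | 0.306 | 37% / 35% | 74% / 69% | 90% / 87% | 0.86 SD | 0.60 SD |

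Across both methods, a 0.5 SD worsening is missed between 100 - 37 = 63% and 100 - 20 = 80% of the time, and a 0.8 SD worsening between 100 - 74 = 26% and 100 - 46 = 54%. A very large comparator does not remove the limit: at n2 = 1,000 the detectable worsening is still 0.78 SD, because the 13 set the precision.

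**Skewed ratings.** Side-effect ratings are likely to contain many zeros, so a second simulation used person-level gamma means (shape 0.7), Poisson session scores capped at 10, and averages over 8 sessions (3,000 runs per cell). With an assumed comparator mean of 0.5 and n2 from 13 to 60, a true doubling is detected 20-32% of the time and a tripling 40-62%.

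**False flags.** If the 11 tests were independent, the chance of at least one false difference in either direction is 1 - 0.95^11 = 43%; for false worsening only it is 1 - 0.975^11 = 24%. Independence is unlikely among items such as tingling, itching and burning.

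**Dropout, exact (Clopper-Pearson) 95% limits.**
- Enrolled: 1/14 = 7.1%, 0.2% to 33.9%.
- Stimulated: 0/13 = 0%, upper limit 1 - 0.025^(1/13) = 24.7%.

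**The case against.** The strongest defence is that the tests are not the whole tolerability assessment. Average ratings on a scale whose top anchor is intolerability speak to tolerability without any comparator, and so does dropout. This stands: the limitation applies to the between-study p-values, not to all the primary-outcome data.

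Four stronger readings are tempting, and the documents do not support them.

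- *That non-significance will be taken as proof of tolerability.* The plan never says so. The gap is that it gives no interval and no other rule.
- *That a clear worsening would probably be missed.* This fits 0.5 SD. At 0.8 SD the simulated test detects the worsening more often than not at three of the four comparator sizes. Without the rating SD, nobody can say which of these counts as clear in rating points.
- *That 1/14 measures dropout from stimulation.* The withdrawal preceded any tACS, so 1/14 bears on feasibility after enrolment, and 0/13 is the figure for those stimulated.
- *That the uncorrected tests are themselves a serious fault.* The plan discloses the choice and gives its reason, and for side effects leaving tests uncorrected favours sensitivity to harm.

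A non-inferiority margin against the earlier study is also open to challenge. That study differs in diagnosis, current, frequency, montage and duration, and a protocol could be worse than a milder one and still tolerable. Not every item is plainly a harm; increased alertness is one of the 11. The text reports the tests as already done, so a margin could hardly be prespecified now. With 13 participants, the power to exclude a 0.5 SD worsening when there is truly none, Phi(0.5/SE - 1.96), is only 25-37%.

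Pilot status excuses a small sample and the absence of multiplicity control. It does not explain leaving out the estimate and interval for a primary outcome, since estimation is what a pilot of this size can deliver.

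**Conclusion.** The point holds as a cheap improvement to the analysis and reporting of a primary outcome. The planned tests are insensitive rather than blind: moderate worsening in a category is usually missed, and large worsening is usually found. The plan's wording is certain on what matters most: 11 difference tests, with no estimate or interval planned for them or for dropout. The size of the problem is less certain. It rests on an assumed comparator size, two-sided testing, normal scores and standardised effects, because the documents supply none of these. The conclusion survives that uncertainty, because the 13 stimulated participants limit precision whatever the comparator size.

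**What to change.** For each of the 11 categories, report this study's ratings on the 0-10 scale and the between-study difference in rating points with a 95% CI: Hodges-Lehmann, or bootstrap or permutation where zeros dominate. Keep the Mann-Whitney p-values as descriptive. State that a non-significant test is not evidence of comparable tolerability, give the comparator's sample size, and list how that study differs (diagnosis, current, frequency, montage and duration).

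Report dropout with exact 95% CIs for both denominators, enrolled and stimulated, noting when the withdrawal occurred. Do not add a between-study margin rule; if a margin is used, label it post hoc.

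The cost is a few sentences in the SAP and a few lines of code on data already held, with no change to trial procedures. The downside is that the intervals will be wide, so the stated conclusion will be less favourable than a list of non-significant p-values might suggest.

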Blood was collected by phlebotomy in EDTA tubes and centrifuged at 2,000 g for 10 min at 4°C. Plasma was then aliquoted in 500 microliter polypropylene tubes, and stored at -80°C until analyses, with an average needle-to-frozen storage time < 2 hours. Plasma was analyzed according to vendor protocols, using commercially available kits Neuro 4-PLEX E [amyloid β_{1-42} (A β 42), amyloid β_{1-40} (A β 40), neurofilament light chain (NfL), and glial fibrillary acidic protein (GFAP)] and P-tau181 for single molecule arrays in an HD-X analyzer (Quanterix, Billerica, MA). Lowest level of quantification and average coefficient of variations were 0.378 pg/mL, 4.1% for A β 42; 1.02 pg/mL, 3.5% for A β 40; 0.4 pg/mL, 4.3% for NfL; 2.89 pg/mL, 4.6% for GFAP; and 0.4 pg/mL, 10.1% for P-tau181. Analyzed samples underwent only one thaw cycle prior to use. Samples were run in duplicate, with kits from the same lot. Following analysis, we were able to measure the picograms per milliliter (pg/mL) of each of the three AD biomarkers at both time points, to quantify stimulation-related changes in AD biomarker levels between the two time points.

Exploratory Behavioral Outcomes.

We examined changes in MDT task performance as a non-registered exploratory measure, focusing on the changes in the lure discrimination index (LDI, proportion lure correct rejection—proportion novel false alarm) between the initial tACS session and final tACS session. Changes in performance were assessed with a Wilcoxon sign-rank test. As the MDT task was completed concurrently with the tACS, it is important to note that changes in MDT performance reflect gains during tACS from repeated test performance, rather than transfer to an untrained task, as with our secondary outcomes. In addition to examining changes in this study population, however, we also compared initial and final LDI performance in these MCI participants to a placebo training control group of healthy older adults from a previous study, where no training-related MDT gains were expected. For this analysis, we compared both initial and final performance between these groups using non-parametric Mann-Whitney U tests.

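### LDI cuts the four-level MDT ratings to two by an unstated rule, ignores target trials and rises with any general shift towards answering 'new'; a lure-versus-target ROC area should sit beside it

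*Combined protocol and SAP*

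**What the plan says.** Under Stimulation Tasks, each MDT test item is answered as "definitely old (“D” key), maybe old (“F” key), maybe new (“J” key), or definitely new (“K” key". A block holds 13 items seen at encoding, "13 items that were an alternate (similar) version of the encoded items, and five novel lures". There are three blocks: "The order of the target, lure, and novel items was random within each of the three testing blocks".

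Under Exploratory Behavioral Outcomes, the analysis is of change in the "lure discrimination index (LDI, proportion lure correct rejection—proportion novel false alarm) between the initial tACS session and final tACS session", tested with a Wilcoxon signed-rank test. Initial and final LDI are also compared, by Mann-Whitney U tests, with healthy older adults who had placebo training in an earlier study. The section calls MDT change exploratory and not registered.

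On numbers, the Participants section says: "Fourteen older adults with aMCI were enrolled and 13 completed the entire intervention in a single-arm design". The other person left before any assessment: "One participant withdrew voluntarily prior to any cognitive assessment or tACS". Data Processing and Statistical Analysis sets the threshold at p < 0.05, describes a hypothesis-generating pilot and makes no multiplicity correction. No power or effect-size assumption is given for LDI.

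The plan does not say which of the four keys count as a correct rejection or a false alarm, and no described analysis uses the confidence grades or the target trials.

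**The concern.** There are two issues, of unequal weight.

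- **Unused information.** Four levels are recorded, two are analysed, and the cut is not given. With 13 pairs, dropping recorded detail may reduce the chance of seeing a real change. An unstated cut also leaves room for the current data and the earlier control data to be scored differently.
- **Response tendency.** LDI does not separate better discrimination from a greater readiness to answer 'new'. Participants take this test in eight sessions, so a change in response habit is possible. If it occurs, LDI would report it as improved lure discrimination.

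**Working it through.** **Inputs from the documents.** Four response levels; 3 blocks × 13 = 39 targets, 39 lures, and 3 × 5 = 15 novel items per session; 13 pairs; Wilcoxon test; 0.05 (two-sided assumed). The per-block reading of the counts fits the 39 encoded items. At 2.5 s viewing plus 1 s fixation, 93 items take 93 × 3.5 / 60 = 5.4 minutes plus responses, which fits the final 10 minutes. The plan gives no power figure to reproduce.

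**Step 1: what LDI measures.** Novel false alarms = 1 − novel correct rejections, so

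LDI = lure CR − novel FA = lure CR + novel CR − 1.

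Someone who answers 'new' to everything scores 1 − 0 = +1; 'old' to everything scores 0 − 1 = −1.

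**Step 2: size of the effect in an assumed model.** Memory strength is normal with SD 1; novel mean 0, lure mean 1.0, target mean 2.0; old/new criterion c = 1.0; confidence cuts at c ± 0.7. Any 'new' answer counts as a rejection. Then lure CR = Φ(c − lure mean) and novel FA = 1 − Φ(c). The area is the chance that a target is rated older than a lure, with ties counted one half.

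| Situation | Lure CR | Novel FA | LDI | Four-level area |
|---|---|---|---|---|
| Start | 0.500 | 0.159 | 0.341 | 0.73 |
| Criterion up 0.3, memory unchanged | 0.618 | 0.097 | 0.521 | 0.74 |
| Lure strength down 0.3, criterion unchanged | 0.618 | 0.159 | 0.459 | 0.79 |
| Target strength up 0.3, all else unchanged | 0.500 | 0.159 | 0.341 | 0.78 |

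The pure criterion shift raises LDI by 0.521 − 0.341 = 0.180, more than the real change in lure memory does (0.459 − 0.341 = 0.118). The area moves by about 0.01 and 0.06 respectively. The last row shows the area's own weakness: it responds to target memory.

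**Step 3: rejection rates under a pure 0.3 criterion shift** (39/15 items, 39 targets where used, n = 13, assumed models of this kind). LDI: 63% to 93% of simulated trials, depending on how much scale use varies. The same lure-novel contrast scored 0–3: 68% to 98%, so grading LDI does not cure it. Lure-target area: about 6% to 10%. With no shift of any kind, all scores rejected in about 4% to 6%.

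**Step 4: power for a true lure shift of 0.3.** Lure mean is 1.0. Set A used 3,000 replicates and set B 1,500. Their base cases differ by up to about 4 points, so compare within rows.

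| Assumption | LDI | LDI contrast, graded | Lure-target, two levels | Lure-target area, four levels |
|---|---|---|---|---|
| A: stable scale use | 0.485 | 0.623 | 0.722 | 0.762 |
| A: criterion SD 0.3 between sessions | 0.194 | 0.190 | 0.618 | 0.719 |
| B: stable scale use | 0.53 | 0.64 | 0.74 | 0.77 |
| B: confidence widths vary (log SD 0.5) | 0.52 | 0.34 | 0.76 | 0.75 |
| B: as above; target strength varies (person SD 0.4, session SD 0.3), criterion SD 0.1, SD of change 0.2 | 0.38 | 0.28 | 0.46 | 0.41 |
| B: as above, but width log SD 0.3 and SD of change 0.4 | 0.29 | 0.28 | 0.28 below two-level 0.32 | 0.28 |

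In the last row the two-level lure-target power is 0.32.

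Effect of grading alone:
- On the LDI contrast: from 0.34 − 0.52 = −0.18 to 0.623 − 0.485 = +0.14.
- On the lure-target contrast: from 0.41 − 0.46 = −0.05 to 0.719 − 0.618 = +0.10.

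In the first row the change of contrast adds 0.722 − 0.485 = 0.24 and grading then adds 0.762 − 0.722 = 0.04.

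**Step 5: the cut matters.** Counting only 'definite' answers gave power from 2 points below to 8 points above the any-new/any-old cut in one set of scenarios. In another, with variable confidence use, it gave 36% against 52%.

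**The case against.** The case for leaving the plan alone is substantial. MDT change is exploratory, the study is a pilot and no power was planned, so none is breached. The documents contain no contradiction here. LDI also has a purpose: it links to the earlier control group, whose graded ratings may not exist. The trial is written up as completed, so a new index would be post hoc and would add one more uncorrected test. All of this stands, and it limits the remedy to an addition.

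A reader might draw four stronger conclusions, and the documents support none of them:

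- *That power is lost by cutting the scale.* The sign of the effect depends on how steadily people use 'maybe' and 'definitely', on which the plan has no data.
- *That a move from maybe new to definitely new counts as no change.* This assumes an any-new cut. Under a definite-only cut the move would count, and the plan states neither.
- *That the ROC area's advantage comes from keeping the grades.* In the stable case most of it comes from replacing novel items with targets, which is a different contrast.
- *That any MDT gain in this trial is a response-habit effect.* Nothing in the documents shows that such a shift occurred.

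The objection does not answer the identity in Step 1, which holds under any cut that treats the complement of a novel false alarm as a correct rejection and needs no power assumption.

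**Conclusion.** The point holds as a minor improvement. It is certain from the text that four levels are recorded, that LDI is a difference of two proportions with no stated cut, and that target trials and grades go unused. It follows by arithmetic that LDI, so scored, rises with a general tendency to answer 'new'.

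The rest is conditional on assumed signal-detection models. The lure-target area is largely insensitive to a criterion shift. Its power was equal to or above that of LDI in nearly every setting tried, with 0.28 against 0.29 the least favourable row above. No fixed power gain should be claimed. If the item counts were totals rather than per block (13 lures, 5 novel), power would be lower under either scoring, for example 0.18 for LDI and 0.24 for its graded form with stable scale use.

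**What to change.** In Exploratory Behavioral Outcomes:

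1. Beside LDI, add the per-participant, per-session area under the lure-versus-target rating ROC. Compute it from the four levels with ties counted as one half, and compare first and last tACS sessions by the Wilcoxon signed-rank test. Label it exploratory or sensitivity, and say that it was added after the data were collected if so.
2. Keep LDI for the control-group comparison. State one rule that maps the four keys to correct rejection and false alarm, and confirm that the same rule was applied to the earlier group.
3. Note that LDI moves with response tendency and that the area moves with target memory, so agreement between them is more informative than either alone.

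The cost is a few lines of scoring code and a few sentences, with no new data. The downsides are one more uncorrected exploratory test on a different contrast, and an index that may not be computable in the earlier control group.
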